19.2. APPENDIX 2: in-vitro study summary

Development of a simple sample processing method for diagnosis of intrathoracic pediatric tuberculosis using Xpert Ultra testing of stool- results of an *in vitro* study.

[name], [name], [name], [name], [name], [name], [name] and [name]

Background

Stool samples are promising alternatives to respiratory samples for molecular diagnosis of childhood tuberculosis (TB) but they require intensive laboratory processing before molecular testing to remove PCR inhibitors and debris. We aimed to develop a centrifuge-free stool processing method for use at peripheral level in resource-limited settings.

Method

In an *in vitro* laboratory study, we tested alternative parameters to optimize a sucrose-flotation method using centrifugation, filtration and vortex shaking that previously showed good sensitivity for childhood TB diagnosis when combined with Xpert: modified amount of stool, manual shaking, no filtration, sedimentation vs centrifugation, modified dilution ratio. Each alternative parameter was compared head-to-head with the reference method using Xpert MTB/RIF Ultra (Ultra) on stool samples spiked with $10^3 M$. *tuberculosis* colony forming units (CFU)/g. We selected the best index methods using a drop-the-loser rule: after 15 tests, methods with invalid/errors > 20% (maximum threshold) were dropped; after 30 tests methods with invalid/errors < 20% and a sensitivity difference with the reference method <10% were kept. For final selection, we tested the best parameters combinations at 10^2 CFU/g. We also assessed methods in terms of quantitative Ultra results (cycle thresholds (CTs)) for MTB detection.

Results

Out of 13 different combinations three were tested at 10^2 CFU/g (Table). The best combination used 0.5g stool, manual shaking, no filtration, 30-minutes sedimentation, and a 1:5 dilution ratio. It had 10% invalid/error results and a sensitivity of 70% (95% CI 50.4-84.5) and 53% (38.8-78.1) vs 63% (43.9-79.4) and 58% (40.7-79.1) as compared to the reference method, at 10^3 and 10^2 CFU/g, respectively.

Discussion

We identified an optimized centrifuge and vortex-free stool sample processing method with potential to facilitate stool Xpert Ultra testing in high burden and resource-limited settings. It should be further evaluated among children with presumptive TB.

Table:

Methods tested at 10 ² CFU/g	- Manual shaking - Sed 30' - 0.5 g - No filtration - dilution ratio 1:5	- Manual shaking - Sed 30' - 1 g - No filtration - ratio 1:5	- Manual shaking - Sed 30' - 0.5 g - Gauze filtration - ratio 1:5
Invalid Index vs reference method	10% vs 6%	11% vs 0%	10% vs 6%
Errors Index vs reference method	0% vs 0%	0% vs 0%	0% vs 0%
Sensitivity* Index vs reference method	53% vs 58%	11% vs 22%	30% vs 58%
Mean CTs IS6110- 1080** Index vs reference method	25.9 vs 27.4	27.2 vs 29.1	26.4 vs 27.4
Mean CTs SPC*** Index vs reference method	28.6 vs 29.1	29.1 vs 29.2	29.1 vs 29.1

* Sensitivity = Proportion of TB detected among all samples; invalid results and errors are counted as negative results.

** CT IS6110-1080 = Cycle thresholds of the two multicopy M. tuberculosis-specific amplification targets (IS6110 and IS1080)

*** CT SPC = Cycle thresholds of the internal Xpert Sample Processing Control

19.3. APPENDIX 3: Description of study sites

COUNTRY	UGANDA
SITE	Mbarara Regional Hospital
CITY	Mbarara, South Western Ankole Region
LEVEL	Regional Referral Hospital
	Teaching Hospital
CATCHMENT AREA	4 000 000 (Region)
(population)	
NB PAEDIATRIC BEDS	100
NB CHILDREN	4 122 in 2017
ADMITTED	
SPECIALIZED WARDS	HIV
	Nutrition Ward
CLINICAL RESEARCH	Yes (HIV, TB, malaria, Yellow Fever)
EXPERIENCE	MSF-Epicentre Research Centre in Uganda
HUMAN RESOURCES	HIV Clinic: 12 staff
TECHNICAL	Laboratory: mycobacteriology, Xpert TB tests, PCR, and routine laboratory
RESOURCES	analyses.

COUNTRY	Z	AMBIA
SITE	University Teaching Hospital, Children's Hospital	Arthur Davidson Children Hospital
CITY	Lusaka - capital city	Ndola, Copperbelt Province
LEVEL	national referral hospital	Provincial Referral Hospital Only standalone peadiatric hospital in Zambia
CATCHMENT AREA (population)	2 000 000 (Lusaka)	2 362 000 (Region)
NB PAEDIATRIC BEDS	352	250
NB CHILDREN ADMITTED	35 000 /year	19 000 /year
SPECIALIZED WARDS	HIV Treatment and Care Centre Nutritional Rehabilitation Unit, Paediatric Intensive care unit, Haematology, Infectious diseases, Cardiac Research Clinic	HIV Treatment and Care Centre Nutritional Rehabilitation Centre TB ward
CLINICAL RESEARCH EXPERIENCE	Yes (HIV) GCP training: all staff from the Research Clinic	Yes
HUMAN RESOURCES	Research Clinic: PI, co-PI, and 15 staff (doctors, research nurses, data managers).	Research staff
TECHNICAL RESOURCES	Laboratory: mycobacteriology, Xpert TB tests, PCR, and routine laboratory analyses.	Laboratory: mycobacteriology, Xpert TB test, microbiology, routine blood tests

19.4. APPENDIX 4: Feasibility assessment tools

Head-to-head comparison of three centrifuge free stool processing methods
Acceptability and feasibility of stool processing methods Self-reported questionnaire for laboratory technicians
ID: Date: // // //

Thank you very much for accepting to participate in this sub-study assessing the ease-of-use of the three stool processing methods in a head-to-head comparison study.

The questions you will answer will help us understand what you think about the stool processing methods. We are interested in knowing about your experience and perception towards these procedures, and what you think about their possible implementation as routine practices in the future.

The questionnaire will take you approximately **20 minutes to complete**.

Each questionnaire is **anonymous**. A unique identification number is used for each participant. All your answers will be kept **confidential** and only aggregated data used to inform stakeholders on the acceptability and feasibility of stool processing methods.

Please remember that there are no wrong or right answers.

When you have completed the questionnaire, please send a scanned copy by e-mail to [contact].

PART 1. Who are you?

1. Job position and education

a) What is your position?

Head of the laboratory
 Laboratory technician
 Laboratory Technologist
 other: please specify.....

a) What is your education level?

b) How many years have you been in this position?

 \Box <1 year

1-3 years

 \Box >3 years

c) How many years of experience do you have handling stool samples prior to starting this study?

- □ no experience
- □ <1 year
- □ 1-3 years
- \Box >3 years

[figure not shown]
d) How many years of experience do you have working in the TB laboratory?

- no experience
 <1 year
 1-3 years
- \Box >3 years

[figure not shown]
e) Have you ever worked or participated in a research project before?

 \Box No \Box Yes

f) When did you start working within this study?

g) When were you trained for each of the methods?

PART 2. Overall experience handling stool as sample for TB diagnosis

Do you agree or disagree with the following statements, irrespective of the method? a) I am comfortable handling stool samples □ Totally agree □ Partially agree Partially disagree □ Totally disagree Please explain: b) I feel that there is no additional biosafety risk in handling stool samples compared to sputum □ Partially agree Partially disagree □ Totally disagree □ Totally agree Please explain: What do you think about a possible routine implementation of stool as a specimen for diagnosing TB in children? a) It would be a good thing □ Totally agree □ Partially agree Partially disagree □ Totally disagree b) It won't improve TB diagnosis in children Partially disagree □ Totally agree □ Partially agree □ Totally disagree c) It should be implemented for all children □ Totally agree Partially disagree □ Totally disagree □ Partially agree d) It isn't realistic in my laboratory Partially disagree □ Totally disagree □ Totally agree □ Partially agree

PART 3 - What do you think about the three centrifuge-free stool processing methods?

1. How would you qualify your overall experience performing the three stool processing methods?

	Poor									Ex	celle	ent	
	0	1	2	3	4	5	6	7	8	9	1	0	
Simple One Step method (SOS):													
Stool Processing Kit (SPK):													
Optimized Sucrose Flotation m	ethod (C	OSF)	: 🗆										

Do you agree or disagree with the following statements regarding the possible advantages or difficulties linked to that procedure?

a) The stool processing is time consuming

SOS:	Totally agree	Partially agree	Partially disagree	Totally disagree
SPK:	Totally agree	Partially agree	Partially disagree	Totally disagree
OSF:	Totally agree	Partially agree	Partially disagree	Totally disagree

b) The stool processing is not difficult to perform

SOS:	Totally agree	Partially agree	Partially disagree	Totally disagree
SPK:	Totally agree	Partially agree	Partially disagree	Totally disagree
OSF:	Totally agree	Partially agree	Partially disagree	Totally disagree
,				
c)	The processing inst	uctions (SOP, OnePage	r) provided are clear	
SOS:	Totally agree	Partially agree	Partially disagree	Totally disagree
SPK:	Totally agree	Partially agree	Partially disagree	Totally disagree
OSF:	Totally agree	Partially agree	Partially disagree	Totally disagree
d)	It requires addition	al equipment and consu	mables compared to spu	itum Xpert processing
, ,	-			
SOS:	Totally agree	Partially agree	Partially disagree	Totally disagree
SPK:	□ Totally agree	Partially agree	Partially disagree	□ Totally disagree
OSF:	Totally agree	Partially agree	Partially disagree	Totally disagree
e)	There is no additi	onal risk (biosafety) fo	or the laboratory staff	compared to Xpert sputum
	processing			
SOS:	Totally agree	Partially agree	Partially disagree	Totally disagree
SPK:	Totally agree	Partially agree	Partially disagree	Totally disagree
OSF:	Totally agree	Partially agree	Partially disagree	Totally disagree
f)	The risk of sample t	o sample contaminatio	n when performing mor	e than one test at the time is
-)	low	P		
606		- Deutielle erner		- Tetella dise sus s
SOS:	□ Totally agree	Partially agree	Partially disagree	□ Totally disagree
SPK:	Totally agree	Partially agree	Partially disagree	Totally disagree
OSF:	Totally agree	Partially agree	Partially disagree	Totally disagree
g)	The risk of environm	ental contamination (e	g spill on the bench) is li	mited
SOS:	Totally agree	Partially agree	Partially disagree	Totally disagree
SPK:	Totally agree	Partially agree	Partially disagree	Totally disagree
OSF:	Totally agree	Partially agree	Partially disagree	Totally disagree
2.	Did you find any of t	he stool processing step	os particularly difficult?	
SOS:	🗆 Yes 🗆 No)		
If yes,	specify the stool proce	essing step(s) and the rea	ason(s):	

SPK: □ Yes □ No

If yes, specify the stool processing step(s) and the reason(s):

 OSF:
 Yes
 No

 If yes, specify the stool processing step(s) and the reason(s):

3. Did you find any of the stool processing steps unnecessary or for which the rationale was not clearly explained?

 SOS:
 □ Yes
 □ No

 If yes, specify the stool processing step(s) and the reason(s):

If yes, specify the stool processing step(s) and the reason(s):

OSF: 🗆 Yes 🗆 No

If yes, specify the stool processing step(s) and the reason(s):

4. Would you have any suggestions to simplify or improve any stool processing method?

SOS:

SPK:

OSF:

Which aspect(s) do you think could be problematic in the day-to-day use of each of the stool processing methods?

Tick all that apply. If nothing applies fill the bottom of the table.

SOS	SPK	OSF
		1

Hands-on time to prepare for processing			
Hands-on time handling the stool specimen			
Total assay time from preparation until Xpert result			
Handling more than one sample at the same time			
Throughput; No of stool specimens processed in one day assuming enough Xpert capacity			
Stool volume requirement (assuming only one test to			
perform)			
Stool volume measurement (use of additional supplies,			
precision)			
Overall number of steps			
Accurate measurement of reagent			
Time-sensitive steps			
Need for additional supplies/reagents compare to Xpert			
sputum testing			
Training requirements			
Storage conditions and stability of reagents (where			
needed)			
Waste management requirements			
If you have ticked none of the options above, why not?			
I see no barriers at all			
I see other barriers, specify for each of the method if needed			
	1	l	1

5. Do you agree or disagree with the following statements regarding user/operator requirements?

a) The procedure is easy to perform for a laboratory staff

b)	, 0	e performed by a NON-	, 0	, 0
OSF:	Totally agree	Partially agree	Partially disagree	Totally disagree
SPK:	Totally agree	Partially agree	Partially disagree	Totally disagree
SOS:	Totally agree	Partially agree	Partially disagree	Totally disagree

SOS:	Totally agree	Partially agree	Partially disagree	Totally disagree
SPK:	Totally agree	Partially agree	Partially disagree	Totally disagree
OSF:	Totally agree	Partially agree	Partially disagree	Totally disagree

c) The procedure could be implemented in a peripheral health center without a laboratory (assuming GeneXpert is available)

SOS:	Totally agree	Partially agree	Partially disagree	Totally disagree
SPK:	Totally agree	Partially agree	Partially disagree	Totally disagree
OSF:	Totally agree	Partially agree	Partially disagree	Totally disagree

d) The procedure could be implemented in a peripheral health center with a microscopy laboratory (assuming GeneXpert is available)

SOS:	Totally agree	Partially agree	Partially disagree	Totally disagree
SPK:	Totally agree	Partially agree	Partially disagree	Totally disagree
OSF:	Totally agree	Partially agree	Partially disagree	Totally disagree

PART 4 – Overall opinion

Considering the ease of use, advantages and disadvantages of each method, which one would you recommend?

If the performance all of the methods was equally good, and you had to use one of the methods, which would be your first choice to perform? Write the number "1" next to your preferred option. Then, enter "2" and "3" for your second and third option respectively. If you value two or more methods equally, use the same number.

SOS:

SPK: _____ OSF: _____

Please explain why:

Which method was easiest to perform?

Write the number "1" next to that method in the list below. Then, consider the remaining methods and continue ranking using "2" and "3" until you've ranked all of the tests. If you consider two or more methods equally easy to perform, use the same number.

SOS: ____

SPK: ____

OSF: ____

Please explain why:

Which method was most difficult to perform?

Write the number "1" next to that method in the list below. Then, consider the remaining methods and continue ranking using "2" and "3" until you've ranked all of the tests. If you consider two or more methods equally difficult to perform, use the same number.

SOS: ____ SPK: ____

OSF:

Please explain why:

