7.6. Feasibility assessment of stool processing methods

Each method will be assessed according their feasibility and ease-of-use. This assessment will be divided in two parts:

- (1) General characteristics of the stool processing method (shelf-life, storage temperature, storage volume, cost, number of steps needed, additional material and equipment needed, health and safety, storage and disposal of waste test materials and reagents, training experience and knowledge needed, interpretation and judgement needed). Each stool processing method will be scored according a rating system laying on the criteria described above [41]. This scoring system will be administering at the end of the study.
- (2) Characteristics related to the opinion of the laboratory technician (rapidity and ease of performance, quality of the instruction sheet, perceived feasibility at each step). The opinion of all the study technicians will be assessed independently and using a short self-administered questionnaire containing open and multiple-choice questions at three time points: after the enrolment of the first 30 children, after enrolment of 150 children (towards the end of the prospective phase) and at the end of the study (Appendix 4). This questionnaire will allow to capture qualitative information related to the perceived utility and feasibility. The questionnaire will be filled online and a study monitor will ensure that the questionnaire is filled independently from the other laboratory technicians involved in the study.

Written informed consent will be obtained from the laboratory technician before administering the questionnaire and scoring system.

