- Stratification of children's characteristics and laboratory results by age groups (<2, 2 to 5, 5 to 10, and >10 years))
- Proportion of children successfully providing a stool sample
- Relative gain of Ultra MTB detection by using ratio of TB detected using 2 stools vs using just the 1st stool specimen for each processing method.
- Description of the results of the ease of use questionnaire for feasibility by technician and time of assessment (beginning, half way and end of the study).

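### The Appendix 4 barrier table offers "other barriers" only when no listed barrier was ticked, and does not say whether that condition applies per method or to the whole table

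*Protocol*

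**What the plan says.** Feasibility is a secondary objective and endpoint (Protocol Sections 2.2 and 3.2). Section 7.6 has two parts: a rating score of general characteristics, and the technicians' opinion, collected "using a short self-administered questionnaire containing open and multiple-choice questions at three time points". The form is to be completed online. Section 11.2.2 plans a "Description of the results of the ease of use questionnaire for feasibility by technician and time of assessment".

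The table at issue is in Part 3 of the questionnaire in Appendix 4. It asks: "Which aspect(s) do you think could be problematic in the day-to-day use of each of the stool processing methods". The columns are the one-step method (SOS), the stool processing kit (SPK) and optimised sucrose flotation (OSF). The completion instruction is "Tick all that apply. If nothing applies fill the bottom of the table".

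The closing block opens with "If you have ticked none of the options above, why not" and then gives two rows: "I see no barriers at all" and "I see other barriers, specify for each of the method if needed".

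**The concern.** In a tick-all-that-apply list, a row for other problems normally adds to the named ones. Here it is placed behind a condition that nothing was ticked. The condition works against the respondents with most to report, because those who have met a listed problem are steered away from naming a further one.

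The condition also has no stated unit. The question is asked for each method, but the instruction and the header of the closing block speak of nothing or none without naming a method. If technicians, or whoever programs the online form, read this differently, the same blank column carries different meanings in different questionnaires. The planned description by technician and time of assessment would then mix them.

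**Working it through.** No arithmetic applies beyond a count; the check is to follow the routing through.

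**Inputs (all from Appendix 4).** Listed aspects: preparation time, handling time, total assay time, handling several samples, throughput, stool volume required, stool volume measurement, number of steps, reagent measurement, time-sensitive steps, extra supplies, training, storage and stability, waste. That is 14 rows for three methods. The table has no other-barrier row outside the conditional block.

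**The two possible readings.**
- Whole-table: the closing rows are for a respondent who ticked nothing for any method.
- Column: the closing rows are for each method whose own column is empty.

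**Routing under each reading.** In the first three rows, take a technician who ticks one listed barrier under SPK.

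| Situation | Whole-table reading | Column reading |
|---|---|---|
| Also sees an unlisted barrier for SPK | Not invited to record it | Not invited to record it |
| Sees only an unlisted barrier for OSF | Not invited to record it | Can record it |
| Sees no barrier for SOS | Not invited to say so; column left blank | Can say so |
| Nothing ticked for any method | Both rows open | Both rows open |

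The first situation fails under both readings, so that loss does not depend on how the form is interpreted. The second and third fail only under the whole-table reading.

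**What a blank column means when another column has a tick.** Under the whole-table reading it can mean no barrier, an unlisted barrier or a skipped column, and the form cannot separate these. Under the column reading the closing rows separate the first two, and a column with no entry at all is simply missing.

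**Which reading the form supports.** The question refers to each method, the columns are per method, and the last row asks for detail by method; these favour the column reading. On the other side, the instruction and the header are not qualified by method, and a request for detail by method also suits a respondent who ticked nothing anywhere. The table was read from a PDF, so its printed layout cannot settle the matter. The unit is ambiguous.

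**Other places to report a problem.** Part 3 has open items by method on difficult steps and on steps that seemed unnecessary or unexplained, and asks "Would you have any suggestions to simplify or improve any stool processing method". Part 4 asks for rankings that weigh advantages and disadvantages, with three free-text explanation fields. None asks directly about barriers to daily use. The step-based items do not naturally draw out problems that are not steps, and none shows why a column was left blank. They are partial outlets.

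**The case against.** The strongest reply is that the table works as intended when read by column, which its layout supports. A technician who ticks SPK can then still mark no barriers for SOS and name another barrier for OSF. This stands as far as it goes: a reader might infer that one tick definitely blocks the closing rows for the other methods, and the form does not say that. The reply leaves the same-method gap untouched, however, and it does not supply the missing unit.

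A second reply is that a blank in such a grid conventionally means the listed aspect was not seen as a problem. That is fair for the 14 listed aspects. It says nothing about unlisted ones, which is what the closing row is for.

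A third reply is that unlisted problems can surface in the open items and in the Part 4 explanations. This also stands in part. It means the information may be recorded elsewhere, so it would be too strong to say that unlisted barriers are suppressed.

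Finally, a reader might infer that the routing tilts the head-to-head feasibility comparison towards methods whose problems are not on the list. The documents do not support that. They give no basis for a direction, they plan no formal comparison of barrier counts, and this table is one item among ratings, agreement statements, rankings and free text, alongside the separate rating score.

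**Conclusion.** The point holds in a narrow form. Followed as written, the table does not invite a technician who ticks a listed barrier for a method to add an unlisted one for that method. This rests only on the instruction and the header of the closing block, and holds under either reading. The unit of the condition is also unstated. If it is read as the whole table, the loss extends to the other methods and a blank column has three possible meanings. That extension is conditional and should not be reported as a certain consequence.

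The size is small and cannot usefully be put as a number, because the Protocol gives no expected frequency of listed or unlisted barriers. It touches one item of a descriptive secondary assessment. Diagnostic accuracy, sample size and error rates are unaffected. It is worth correcting because the wording is plainly unhelpful and the correction is easy.

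**What to change.** In the Appendix 4 table:

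1. Delete the instruction to fill the bottom only if nothing applies, and the header that asks why none was ticked.
2. Make other barrier (specify) an ordinary row, open to every respondent in each method's column whatever was ticked above.
3. Make no barriers a separate tick for each method.
4. State that a column with no tick and no entry in either closing row counts as missing, and have the online form query a column that carries both a barrier and the no-barriers tick.

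The cost is the rewording of two rows and, at a rough estimate, under a minute more per respondent. No visit, sample or analysis is added. Section 17 requires a written amendment for any change to the protocol, so the edit is best carried with the next one. If an earlier assessment has already used the present wording, describe this item separately by form version, and do not read a blank column on the old form as absence of barriers.
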